3.6 Sample Size

This study is a non-inferiority design, and the primary outcome is the occurrence of skin bacterial colonization on the seventh or eighth day after CVC catheterization (binary outcome). The sample size is calculated based on the difference between the two groups of the primary outcome.

According to our previous pilot study that included 49 subjects, the occurrence of skin bacterial colonization in the CD7d group and the CD24h group was 56.3% and 55.6%, respectively. A non-inferiority margin of 20% is considered to be clinically acceptable. Based on the assumptions of (i) the occurrence of skin bacterial colonization of 55% in the CD24h group, (ii) the non-inferiority margin of 20%, (iii) power of 80%, and (iv) a one-sided alpha of 0.025, the sample size estimation resulted in 98 subjects per group (calculated with PASS software, version 16.0). Considering a 30% drop-out rate, a total of 280 subjects should be randomized (140 per group).

4. Analysis Populations

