5.1. Primary Outcome Analysis

5.1.1 ITT analysis of the primary outcome - the primary analysis

The primary outcome is a binary outcome: the occurrence of skin bacterial colonization on the seventh or eighth day after CVC catheterization. The primary analysis will be based on the ITT population as defined above.

Hypothesis: Let π_1 denote the occurrence of skin bacterial colonization on the eighth day after CVC catheterization in the CD24h group (control group), and let π_2 denote the occurrence of skin bacterial colonization on the seventh day in the CD7d group (experimental group), the non-inferiority margin $\Delta=20\%$. The null hypothesis is $H_0: \pi_2 - \pi_1 > \Delta$ versus the alternative hypothesis is $H_A: \pi_2 - \pi_1 \leq \Delta$.

A generalized linear model (GLM) will be used to test the above hypothesis. In the GLM, the occurrence of skin bacterial colonization will be treated as the dependent variable and the treatment as the fixed effect, following a binomial distribution and identity link function. A point estimate of risk difference between groups in the difference and its 95% confidence interval (CI) will be estimated. CD7d treatment will be considered non-inferior to the CD24h treatment if the upper 95% confidence limit is no greater than Δ , where $\Delta= 20\%$, the predetermined non-inferiority margin.

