5.1.2 Sensitivity analyses of the primary outcome

- PP analysis with GLM (described in 5.1.1) will be performed.
- An analysis of the primary outcome will be adjusted for age, gender, CVC catheterization site, type of disease, and administration set at baseline in ITT and PP population, respectively. The adjusted difference and 95% one-sided upper limit comparing the two groups will be derived by GLM (described in 5.1.1). If the above identity-binomial GLM does not converge when all covariates are introduced into the model, the adjusted model will be performed by removing a covariate one by one until the model converges.

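### Optional gain in precision: the deciding analysis in SAP 5.1.1 contains treatment only, although age, catheter site and disease type are collected and already serve as adjustment covariates in 5.1.2

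*SAP*

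**What the plan says.** Section 5.1.1 of the SAP sets the primary analysis: a binomial model with identity link in which "the occurrence of skin bacterial colonization will be treated as the dependent variable and the treatment as the fixed effect". No other term enters. The upper limit of the 95% interval for the risk difference is compared with 20%.

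Section 5.1.2 then states, as a sensitivity analysis: "An analysis of the primary outcome will be adjusted for age, gender, CVC catheterization site, type of disease, and administration set at baseline". If that identity-link model fails to converge, "the adjusted model will be performed by removing a covariate one by one until the model converges". The result is reported as "The adjusted difference and 95% one-sided upper limit comparing the two groups". Table 2 in section 6.2 puts the adjusted results in its sensitivity rows.

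Three of these covariates recur elsewhere. Age, disease type and catheter site are the covariates of the adjusted Cox model for MARSI (5.2.2), and disease type defines a subgroup for the primary outcome (5.1.3). Baseline Table 1 reports all three. The variable list in section 7 holds date of birth, catheter site and diagnosis. Administration set is in neither place. Section 3.4 names no stratification factor. Section 3.6 sets 98 evaluable per arm with no allowance for covariates.

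**The concern.** With a binary outcome and about 98 evaluable children per arm, the decision depends on an interval that reaches about 14 points either side of the estimate, against a margin of 20. If baseline factors explain part of the outcome, an analysis that uses them narrows the interval and removes the effect of chance imbalance in those factors, with no extra child recruited. The SAP has picked such factors and will hold the data, but lets them inform only estimates that decide nothing.

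At stake are a few points of power in a trial planned at 80%. The opportunity is also limited in time. The deciding estimate can be chosen without suspicion only before the study team receives the allocation, which section 3.5 places after database lock.

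**Working it through.** **Inputs.** From SAP 3.6: "the occurrence of skin bacterial colonization of 55% in the CD24h group", margin 20 points, power 80%, "a one-sided alpha of 0.025", 98 evaluable per arm, 30% drop-out. The experimental rate used in the calculation is not stated; a true difference of zero is assumed because it reproduces the plan's figure. R2, the share of outcome variance explained by baseline covariates, is not in the SAP and is varied.

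**1. The plan's own figure.** n per arm = (0.55×0.45 + 0.55×0.45) × (1.960 + 0.842)² / 0.20² = 97.13, rounded up to 98. 98 / 0.70 = 140 per arm, 280 in total. Both agree with the SAP.

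**2. The unadjusted analysis at 98 per arm.** SE = sqrt(0.495/98) = 0.0711. Half-width = 1.96 × 0.0711 = 13.9 points. Power = Φ(0.20/0.0711 − 1.96) = 80.4%.

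**3. What adjustment could give.** In large samples the variance is multiplied by (1 − R2). Estimating the covariate effects has a cost. The three covariates use 1 (age) + 2 (three sites) + 3 (four disease groups) = 6 degrees of freedom, so a rough correction multiplies the variance by (196 − 2)/(196 − 8) = 194/188 = 1.032.

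| R2 (assumed) | Half-width, uncorrected | Power, uncorrected | Half-width, corrected | Power, corrected |
|---|---|---|---|---|
| 0 | 13.9 | 80.4% | 14.1 | 79.1% |
| 3% | 13.7 | 81.5% | 13.9 | 80.3% |
| 7% | 13.4 | 83.1% | 13.6 | 81.9% |
| 8% | 13.4 | 83.5% | 13.6 | 82.3% |
| 12% | 13.1 | 85.1% | 13.3 | 84.0% |
| 15% | 12.8 | 86.3% | 13.0 | 85.2% |

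On this approximation break-even lies at R2 = 6/194 = 3.1%. Below that, adjustment costs slightly more than it returns.

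**4. Simulation.** Trials with 98 per arm, a three-level site, a four-level disease type and continuous age compared the unadjusted difference with one standardized from a logistic model.
- Power, 3000 trials per setting: 80.0% v 80.7% at R2 of 3%, 80.0% v 83.0% at 7%, 78.8% v 84.7% at 12%. Type I error at a true difference of +20 points: 2.4% v 2.4%, 2.6% v 2.5%, 2.8% v 2.9%.
- With a degrees-of-freedom-corrected SE: about 80% v 81% at R2 of 3%, 80% v 83% at 8% and 80% v 86% at 15%, with type I error of 2.2% to 2.9%.
- At R2 of 0 the adjusted estimate was slightly more variable (empirical SE 0.0727 v 0.0715, a ratio of 1.017, in line with sqrt(194/188) = 1.016). The uncorrected influence-function interval was nevertheless narrower (half-width 13.6 v 13.9 points), which is too narrow. A further run of 4000 trials per setting gave that uncorrected interval a type I error of 3.3% v 2.75% at R2 of 0, and 3.0% v 2.5% at about 4%.

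**5. Whether the 5.1.2 model could serve.** Its fallback removes covariates in no stated order. In an illustrative simulation with all five covariates (600 runs, R2 about 11%), a linear identity-scale fit stayed between 0 and 1 in only about 20% of runs, so convergence trouble is plausible. Its limit, read literally, uses 1.645 in place of 1.96: at the unadjusted SE, 1.645 × 0.0711 = 11.7 points in place of 13.9. That is one-sided 0.05, against the 0.025 of section 3.6.

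**The case against.** The strongest reply is that nothing here is wrong. Section 5.1.1 is fully specified, an unadjusted risk difference is valid under 1:1 randomization, and it matches the sample size calculation, which used no covariates. The interval already allows for chance imbalance, and the adjusted estimates will appear beside the deciding one in Table 2. No factor is named as a stratifier, so the design does not oblige adjustment. All of this stands, and it is why the point is an improvement and not a defect.

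It can also be said that the SAP never calls these factors prognostic and reports no association with colonization. That stands too. A reader might infer from their place in 5.1.2 that they are known predictors and that precision is certainly lost. The document does not support this: choosing a covariate for a sensitivity analysis does not show that it matters, and with R2 near zero there is nothing to gain.

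Finally, an adjusted primary analysis can do harm if loosely specified. The uncorrected interval was slightly too narrow in simulation, and a model that drops covariates as needed would put a data-driven choice into the deciding test. This argues for a fixed covariate list and a corrected variance; it does not argue against adjustment. Centre, which is recorded and within which the blocks are used, is a separate question not settled here.

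**Conclusion.** The point holds as a low-cost, optional improvement. The deciding model leaves out three covariates that the SAP plans to collect and already uses elsewhere, and precision may be forgone as a result. The size depends wholly on an assumed R2: essentially nothing at 0 to 3%, about 2 to 3 power points at 7 to 8%, and about 4 to 6 at 12 to 15%. These figures also assume 55% colonization in both arms and 98 evaluable children per arm.

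Two stronger readings should be resisted. The primary analysis is not biased, invalid or underpowered on the plan's own assumptions: it gives 80.4%. Nor is the remedy to move the 5.1.2 model up to primary, since its covariate set is not fixed and its one-sided limit does not match the alpha of section 3.6.

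**What to change.** Amend section 5.1.1 before allocation is revealed:
- Make the primary estimate the marginal risk difference (CD7d minus CD24h) standardized from a logistic model with arm, age as a continuous term, catheter site and disease type. The list is fixed, with no data-driven removal. These are the same three covariates as in the adjusted MARSI model, and all are on the variable list.
- Give a two-sided 95% interval from an influence-function or delta-method variance with a degrees-of-freedom correction, and compare its upper limit with 20%. The estimand and the margin do not change.
- Keep the present unadjusted identity-link model as the first sensitivity row of Table 2.

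The cost is a paragraph of SAP text and a few lines of code, with no new data and no change to the sample size. The downside is a slightly less simple primary model and, if the covariates carry no information, a negligible loss of precision: about 1.6% on the SE, or roughly one power point by the approximation above.

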5.1.2 Sensitivity analyses of the primary outcome

- PP analysis with GLM (described in 5.1.1) will be performed.
- An analysis of the primary outcome will be adjusted for age, gender, CVC catheterization site, type of disease, and administration set at baseline in ITT and PP population, respectively. The adjusted difference and 95% one-sided upper limit comparing the two groups will be derived by GLM (described in 5.1.1). If the above identity-binomial GLM does not converge when all covariates are introduced into the model, the adjusted model will be performed by removing a covariate one by one until the model converges.

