6.2 Graphical / Table Displays

Figure 1: Patient flow chart. A patient disposition flow chart will be presented showing the number of patients randomized to each treatment arm, reasons for withdrawal, and numbers available for each analysis population.

Table 1. Baseline characteristics of patients

Characteristics	Statistics	CD7d treatment (N=)	CD24h treatment (N=)
Age (year)	Mean(SD)		
Height (cm)	Mean(SD)		
Weight (kg)	Mean(SD)		
Birth weight (kg)	Mean(SD)		
Gender, n (%)	Female		
	Male		
Admission disease diagnosis, n (%)	Congenital heart disease		
	Congenital biliary atresia		
	Tumor		
	Others		
CVC catheterization site, n (%)	Jugular		
	Subclavian		
	femoral		

Table 2. Primary outcome of occurrence of bacterial colonization by treatment

Population	Occurrence of bacterial colonization (95% CI)		Difference (95% CI)	Non-inferiority P value
	CD7d treatment (N=)	CD24h treatment (N=)		

Primary analysis:

ITT population

Sensitivity analysis:

PP population

Adjusted analysis (ITT)^{*}

Adjusted analysis (PP)[#]

* The analysis will be adjusted for age, gender, CVC catheterization site, type of disease, and administration set in the ITT population.

The analysis will be adjusted for age, gender, CVC catheterization site, type of disease, and administration set in the PP population.

Table 3. Summary of generalized linear model analysis of secondary outcomes

Outcomes	Incidence (95% CI)		Difference (95% CI)	P value
	CD7d treatment (N=)	CD24h treatment (N=)		

Incidence of CLABSI**Table 4. Proportion hazards models for time-to-event outcomes**

Outcomes	Incidence (95% CI)		Hazard ratio (95% CI)	P value		
	CD7d treatment (No. of events / No. of patients)	CD24h treatment (No. of events / No. of patients)				
Incidence of MARSI						
Unadjusted analysis						
Adjusted analysis*						

* The analysis will be adjusted for age, disease type, and CVC catheterization site.

7. Study variable list

Variable	Variable interpretation	Variable Type
center	Name of center	Text
center_no	Number of center	Text
name	Initials of subject	Text
id	Study ID of subject	Number
date_start	Date of enrollment	Date
date_end	Date of end	Date
investigator	Initials of investigator	Text
arm	Intervention allocation	Categorical
date_birth	Date of birth	Date
gender	Male / Female	Binary
height	Height at baseline	Continuous
weight	Body weight at baseline	Continuous
birth_weight	Body weight at birth	Continuous
cathete_site	Jugular/ Subclavian/ femoral	Categorical

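### SAP 5.1.2 gives the adjusted analyses a one-sided 95% upper limit (one-sided 0.05), although the trial is sized at one-sided 0.025 and Table 2 plans a 95% CI for the same rows

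*SAP*

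**What the plan says.** - **Section 3.6 (Sample Size)** uses "a one-sided alpha of 0.025", with 80% power, a 20% margin and "the occurrence of skin bacterial colonization of 55% in the CD24h group". The result is 98 per group, raised to 140 per group for 30% drop-out.
- **Section 5.1.1 (primary analysis)** fits a binomial GLM with identity link: "A point estimate of risk difference between groups in the difference and its 95% confidence interval (CI) will be estimated". Non-inferiority is declared if the upper 95% confidence limit does not exceed 20%.
- **Section 5.1.2 (sensitivity analyses)** covers the covariate-adjusted ITT and PP analyses: "The adjusted difference and 95% one-sided upper limit comparing the two groups will be derived by GLM (described in 5.1.1".
- **Section 6.2, Table 2** has one column headed "Difference (95% CI" that serves every row, including "Adjusted analysis (ITT" and its PP counterpart. A footnote confirms that the PP row is the same covariate-adjusted model: "The analysis will be adjusted for age, gender, CVC catheterization site, type of disease, and administration set in the PP population". The next column is "Non-inferiority P value", with no level given.

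**The concern.** A one-sided 95% upper limit and the upper end of an ordinary 95% CI are different numbers. The first corresponds to one-sided 0.05, the second to one-sided 0.025. The direct clash is between 5.1.2 and the adjusted rows of Table 2, which are the same output. Section 5.1.1 covers the unadjusted primary analysis, but 5.1.2 refers back to its model, and that model is reported with a 95% CI. Nothing in the SAP explains a looser level for the adjusted rows.

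The adjusted analyses are there to show whether the primary finding is robust, and readers will hold them against the same 20% margin. If the analyst follows 5.1.2, an adjusted result that misses the margin at the design level can appear with a limit below 20%, as support for a passing primary. If the analyst follows Table 2, only the text is inconsistent. The choice between the two could be made after the results are seen.

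**Working it through.** **1. Which level the design uses.** Inputs from section 3.6: 55% in the control arm (taken as equal in both arms), margin 0.20, power 80% (z = 0.8416). Per-arm size: n = (z_alpha + 0.8416)² × 2 × 0.55 × 0.45 / 0.20².

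- One-sided 0.025 (z = 1.960): 97.1, so 98 per arm; 98/0.70 = 140. Both stated figures are reproduced.
- One-sided 0.05 (z = 1.645): 76.5, so 77 per arm; 77/0.70 = 110.

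**2. Gap between the two limits.** SE = √(2 × 0.55 × 0.45 / n); gap = (1.960 − 1.645) × SE.

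| Evaluable per arm | SE | Gap | Gap if adjusted SE is 0.9 to 1.2 times this (assumption) |
|---|---|---|---|
| 98 | 0.0711 | 2.2 points | 2.0 to 2.7 points |
| 140 (no drop-out) | 0.0595 | 1.9 points | 1.7 to 2.2 points |

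At 98 per arm the limit lies 11.7 points above the estimate under 5.1.2 and 13.9 points above it at the design level. The largest difference that stays within 20% is therefore 8.3 points under 5.1.2 and 6.1 points at the design level. Estimates between those values change sides.

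**3. Example with a passing primary.** Control 54/98, experimental 59/98:

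- Difference 0.0510, SE 0.0705; upper limit 0.0510 + 1.960 × 0.0705 = 0.189, so the primary passes.
- Suppose the adjusted difference is 0.070 with the same SE (assumption).
- Limit under 5.1.2: 0.070 + 1.645 × 0.0705 = 0.186, below 20%.
- Upper end of the 95% CI: 0.070 + 1.960 × 0.0705 = 0.208, above 20%.
- One-sided P = Φ((0.070 − 0.20)/0.0705) = 0.033, above 0.025.

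**4. How often this could happen.** The event is that the primary passes while the adjusted limit is within 20% at one-sided 0.05 but not at 0.025. The calculation treats the unadjusted and adjusted estimates as bivariate normal, with 98 per arm and a control rate of 55%. The SAP gives neither the correlation nor the ratio of standard errors, so both are assumptions.

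With equal SEs:

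| True difference | Correlation 0.90 | 0.95 | 0.98 | P(primary passes) | Share of passing primaries |
|---|---|---|---|---|---|
| 0 | 3.4% | 2.9% | 2.1% | 80.35% | 2.6% to 4.3% |
| 5 points | 4.7% | 4.0% | 3.0% | 56.62% | 5.2% to 8.2% |

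A simulation of 3 million draws agrees at correlations 0.90 and 0.98 (3.45% and 2.09% at true difference 0; 4.64% and 2.95% at 5 points). At true difference 0 the chance is 0.1% to 1.2% if the adjusted SE is 0.9 times the unadjusted one, and 8.6% to 10.1% if it is 1.2 times.

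**The case against.** The strongest reply is that this touches only two sensitivity rows. No decision rule is attached to them, the unadjusted PP analysis follows 5.1.1, and no prespecified conclusion depends on the phrase. The table shell already plans a 95% CI, so harm requires departing from it. A different level in a sensitivity analysis does not in itself contradict the sizing of the primary comparison. All of that stands, and it limits the weight of the point. It does not remove the contradiction, because 5.1.2 is the operative text for these analyses and Table 2 disagrees with it.

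It can also be said that the probabilities in step 4 rest on unstated quantities and run from 0.1% to 10.1% at true difference 0. That is fair. They illustrate the possible size, and the point does not depend on them. The gap of about 2 points follows from the SAP's own figures once the adjusted SE is taken as close to the unadjusted one.

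Finally, 5.1.1 never says two-sided, so its own limit could be read loosely. A 95% CI without qualification is conventionally two-sided, and only that reading matches the sizing alpha. The looseness is a reason to clarify 5.1.1 as well, not a defence of 5.1.2.

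**Conclusion.** The point holds: section 5.1.2 is wrong as written and should be fixed. Taken literally, it sets the adjusted limits at one-sided 0.05, twice the design alpha, and conflicts with Table 2 for the same rows. The limit is about 2.2 points too favourable at 98 evaluable per arm and 1.9 points at 140, assuming rates near 55% and an adjusted SE equal to the unadjusted one. The effect is confined to how the adjusted sensitivity analyses are presented. The primary conclusion and the sample size do not change, and a drafting slip is a plausible cause.

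**What to change.** In 5.1.2, replace the one-sided 95% upper limit with a two-sided 95% CI whose upper end is the one-sided 97.5% limit. State that the non-inferiority P values in Table 2 are judged at one-sided 0.025. Adding the word two-sided to the 95% CI in 5.1.1 is an optional clarification that could go into the same edit.

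The cost is a one-line change to the SAP, with no new data, patients or modelling. The adjusted upper limits become about 2 points higher.

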5.1.3. Subgroup analyses of the primary outcome

Subgroup analyses for the primary outcome will be performed using GLM. We will stratify by gender and disease type. Gender will be divided into male and female. Disease type will be divided into congenital heart disease, congenital biliary atresia, tumor and others. Subgroup analyses will be performed if each subgroup contains enough patients after stratification.

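### Section 5.1.3 stratifies the primary outcome by gender and disease type without an arm-by-subgroup interaction, so it cannot test whether the effect differs between subgroups

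*SAP*

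**What the plan says.** Section 5.1.3 is the whole subgroup plan. It names a GLM for the primary outcome and continues: "We will stratify by gender and disease type". The levels are fixed: "Gender will be divided into male and female", and "Disease type will be divided into congenital heart disease, congenital biliary atresia, tumor and others". One condition is attached: "Subgroup analyses will be performed if each subgroup contains enough patients after stratification". No number defines what is enough.

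The section names no interaction term, no heterogeneity test and no rule for reading a subgroup result. The margin rule stands in section 5.1.1, for the overall comparison: "CD7d treatment will be considered non-inferior to the CD24h treatment if the upper 95% confidence limit is no greater than Δ", with the margin at 20 points. The model there has treatment as its only effect, "following a binomial distribution and identity link function", so it estimates a risk difference.

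**The concern.** A subgroup analysis is meant to show whether the treatment effect is similar across groups. Estimates made stratum by stratum do not answer that. Two intervals can differ in position or width because one stratum is small, and comparing each with a fixed threshold is not a comparison of the strata with each other.

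At stake is how a successful trial would be read. Suppose the overall result met the margin while the interval for one diagnosis crossed 20 points. With no heterogeneity test and no statement on interpretation, a reader could conclude that the 7-day dressing is acceptable in some diseases and not in others, when only precision differs.

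**Working it through.** **Inputs.** From SAP section 3.6: "the occurrence of skin bacterial colonization of 55% in the CD24h group", margin 0.20, one-sided alpha 0.025, power 80%, 98 evaluable per arm, 30% drop-out and 140 randomized per arm. From 5.1.3: two gender levels and four disease levels. Assumed here: 55% in the CD7d arm as well (identical arms), equal subgroup sizes (the SAP gives no shares), and 1.96 for the upper limit, in line with one-sided 0.025.

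**The plan's own figure.** n per arm = (1.960 + 0.842)² × 2 × 0.55 × 0.45 / 0.20² = 97.1, rounded up to 98. Then 98 / 0.70 = 140. Both agree with section 3.6.

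**Chance of meeting the margin with identical arms.** SE = sqrt(2 × 0.55 × 0.45 / n) and chance = Φ(0.20/SE − 1.96).

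| Group | n per arm | SE | 0.20/SE − 1.96 | Chance of meeting 20 points |
|---|---|---|---|---|
| Whole trial | 98 | 0.071 | 0.85 | 80% |
| Gender half | 49 | 0.101 | 0.03 | 51% |
| Disease quarter | 24.5 | 0.142 | −0.55 | 29% |

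**At least one group misses.** Strata within a factor share no patients, so the chances multiply.
- Gender: 1 − 0.512² = 74%.
- Disease type, all four groups analysed: 1 − 0.290⁴ = 99.3%.

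**Simulation check** (100,000 trials, identical arms, Wald limits):
- With 98 per arm and equal splits, at least one of the six groups misses in 98.8% of trials. Among trials that meet the margin overall, the figure is 98.5%.
- Unequal disease splits (70/10/10/10, 40/30/20/10, 85/5/5/5) give 99.5–99.8%.
- With all 140 per arm evaluable and equal splits, the figure is 97.8% for all six groups and 56% for gender alone.
- With common rates of 30–65%, over both sample sizes, it is 95.6–98.9% for all six.

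**What an interaction test would show.** In simulated identical arms, a test at the 5% level signals heterogeneity in about 5% of trials for gender (1 df) and 6–7% for disease type (3 df). At least one of the two signals in about 11–12%.

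**What it would not change.** A model with arm, one factor and their product is saturated. Its subgroup risk differences and intervals are therefore those of separate fits, and their widths stay the same.

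**Power of the test.** For gender, the SE of the difference between two risk differences is sqrt(2) × 0.1005 = 0.142, using the variance at 55% throughout. For 80% power at two-sided 5%, the true risk differences in boys and girls would have to lie about 2.80 × 0.142 = 0.40 apart, that is, 40 points.

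**The case against.** A reader might infer something stronger: that the SAP will judge each subgroup against 20 points, and that because the interaction is missing, identical arms will almost surely produce a subgroup that fails non-inferiority. The document does not support this, for three reasons.

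- **The margin is not carried into 5.1.3.** Section 5.1.2 refers back to the 5.1.1 model explicitly when it reuses it; 5.1.3 says only GLM. Planned Table 2, which holds the non-inferiority P values, has rows for ITT, PP and the two adjusted analyses, and none for subgroups. No other planned table covers them.
- **The missing interaction does not cause the misses.** They come from small strata, and adding the term leaves the 74% and 99% unchanged.
- **The 99% figure needs all four disease groups to pass the condition on patient numbers.** If only gender were analysed, the figure would be about 56–74%, depending on how many of the 140 per arm are evaluable.

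It can also be said that 5.1.3 neither states that the fits are separate nor rules out an interaction term. That is true, but stratification by factor is most naturally read as separate fits, and no between-stratum test is specified under any reading. The subgroups bear on no primary conclusion, which keeps the point small.

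What stands is that the stated method does not test whether the effect differs between subgroups, and that the section does not say how its estimates are to be read.

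**Conclusion.** The point holds as a cheap improvement. As written, 5.1.3 leaves only within-stratum intervals to compare, and these cannot show whether the treatment effect varies by gender or disease type.

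The percentages are conditional. They measure what would happen if a reader applied the 5.1.1 margin inside each subgroup, with no true difference, a 55% rate in both arms, 98 evaluable per arm and equal splits. They show how misleading that reading would be; they do not measure an error in a verdict that the SAP plans. The disease-type figure is stable over the splits, rates and sample sizes tried. The gender figure is more sensitive to the evaluable number. The primary analysis and its conclusion are untouched.

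**What to change.** In section 5.1.3:

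1. For each factor, fit one binomial GLM with identity link containing arm, subgroup and arm-by-subgroup terms.
2. Report the interaction test (1 df for gender, 3 df for disease type) beside the subgroup risk differences and their 95% CIs, labelled exploratory.
3. State that no non-inferiority verdict is drawn within any subgroup.
4. State that the interaction test has low power, so that a non-significant result is not evidence of a uniform effect.

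A numeric minimum for the condition on patient numbers would be a useful addition.

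The cost is a few sentences and one interaction per factor. Data collection, sample size and the primary analysis do not change. The subgroup intervals stay as wide as before; the gain is in how they are read.
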